Appendix A. Schedule of Assessments – Part B

Study Period (or Dose #)	Screen	Lead-In	Dose 1		Dose 2	Dose 3	Dose 4	Dose 5	Dose 6	Dose 7	Dose 8
Study Week	≤ 42 days		1		2	3	4	5	6	7	8
Study Day		1 to 2 Weeks	Baseline/ Pre-dose	1	8 ± 1	15 ± 1	22 ± 1	29 ± 1	36 ± 1	43 ± 1	50 ± 1
Informed consent	X										
Medical History ^a	X		X								
Physical examination	X		X					X			
Height (Screening only) & Body weight	X	X	X					X			
Urine pregnancy test (women); FSH ^f	X		X					X			
Urine drug/alcohol test	X		X					X			
12-lead ECG ^b	X		X					X			
Vitals (BP, RR, HR, T) ^c	X	X	X		X	X	X	X	X	X	X
Chemistry, Hematology, Lipid Panel, and Urinalysis ^e	X		X		X	X		X		X	
Fasting (≥ 8-hr) plasma glucose ^e			X		X	X	X	X	X	X	X
Serum Ketones & Free Fatty Acids ^e			X		X	X	X	X	X	X	X
Study Drug SC Administration				X	X	X	X	X	X	X	X
Seven-point blood glucose profile ^d		X					X				X
Blinded Continuous Glucose Monitoring (CGM) ^g		X		X			X				X
Daily insulin usage dairy ^h		X	X	X	X	X					X
HbA1c	X		X						X		
Insulin, C-peptide, GLP-1, and Glucagon ^e			X					X			
Serum PK sample collection ^e			X		X			X			
Anti-REMD-477 Ab sample collection ^e			X								
Exploratory biomarker collection ^e			X								
Liver Injury Biomarkers ^e			X					X			
Liver MRI/ FibroScan ^j			X								
QOL Questionnaires ⁱ			X								
Con-Med monitoring	X		◀	▶							
Adverse event monitoring			◀	▶							

Footnote Key:

- a. Medical history includes significant past medical events (e.g. prior hospitalizations or surgeries), a review of diabetes history and glycemic control, and any concurrent medical illnesses.
- b. After the Screening Visit, 12-lead ECG to be performed in triplicate, approximately 1 min apart. When ECG and blood sample collection occur at the same time, ECGs should be performed before blood samples are drawn.
- c. Vital signs include blood pressure, respiratory rate, heart rate, and oral temperature.
- d. Seven-point blood glucose profile will measure glucose by finger stick over three consecutive days before and 2 hours after each meal, and at bedtime.
- e. Sample should be collected pre-dose on all dosing days.
- f. FSH required at screening for post-menopausal women.
- g. Blinded CGM will be performed for one week during the Lead-in Period (completed prior to the Baseline Visit), and for one week after Doses 1, 4, 8 and 12. CGM data will be downloaded at the clinical research unit during scheduled site visits, as indicated in the Schedule of Assessments.
- h. Subjects will be given insulin usage diaries during the Lead-in Period and at the beginning of Weeks 1 through 4, 8, 12, 16, and 20. For one week of the Lead-in Period and Weeks 1 through 4, daily insulin use (short-acting, long-acting, and infusional as applicable) will be collected over seven days. For Weeks 8, 12, 16, and 20, daily insulin will be collected over a period of 3 consecutive days within that respective week.
- i. The *WHO-5 Well-Being Index & T1-DDS QOL* Questionnaires will be completed by the subjects at the Baseline, Day 84, and Day 161.
- j. Both the Liver MRI and FibroScan Baseline Assessments may be performed up to 7 days before the Day 1 Visit, after all other inclusion and exclusion criteria have been met.

Schedule of Assessments – Part B

Study Period (or Dose#)	Dose 9	Dose 10	Dose 11	Dose 12	Follow-up Period			EOS
Study Week	9	10	11	12	13	16	20	24
Study Day	57 ± 1	64 ± 1	71 ± 1	78 ± 1	85 ± 2	106 ± 2	134 ± 2	162 ± 2
Informed consent								
Medical History ^a								
Physical examination					X			X
Body weight	X				X	X	X	X
Urine pregnancy test (women); FSH ^f	X				X			X
Urine drug/alcohol test								X
12-lead ECG ^b	X		X		X			X
Vitals (BP, RR, HR, T) ^c	X	X	X	X	X	X	X	X
Chemistry, Hematology, Lipid Panel, and Urinalysis ^e	X				X			X
Fasting (\geq 8-hr) plasma glucose ^e	X	X	X	X	X			X
Serum Ketones & Free Fatty Acids ^e	X	X	X	X		X	X	
Study Drug SC Administration	X	X	X	X				
Seven-point blood glucose profile ^d				X		X	X	
Blinded Continuous Glucose Monitoring (CGM) ^g				X				
Daily insulin usage diary ^h				X		X	X	
HbA1c					X			X
Insulin, C-peptide, GLP-1, and Glucagon ^e	X				X	X		X
Serum PK sample collection ^e	X				X	X		
Anti-REMD-477 Ab sample collection ^e					X			X
Exploratory biomarker collection ^e					X			X
Liver Injury Biomarkers ^e	X				X	X		
Liver MRI/FibroScan ^j					X			
QOL Questionnaires ⁱ					X			X
Con-Med monitoring	↔							→
Adverse event monitoring	↔							→

Footnote Key:

- a. Medical history includes significant past medical events (e.g. prior hospitalizations or surgeries), a review of diabetes history and glycemic control, and any concurrent medical illnesses.
- b. After the Screening Visit, 12-lead ECG to be performed in triplicate, approximately 1 min apart. When ECG and blood sample collection occur at the same time, ECGs should be performed before blood samples are drawn.
- c. Vital signs include blood pressure, respiratory rate, heart rate, and oral temperature.
- d. Seven-point blood glucose profile will measure glucose by finger stick over three consecutive days before and 2 hours after each meal, and at bedtime.
- e. Sample should be collected pre-dose on all dosing days.
- f. FSH required at screening for post-menopausal women.
- g. Blinded CGM will be performed for one week during the Lead-in Period (completed prior to the Baseline Visit), and for one week after Doses 1, 4, 8 and 12. CGM data will be downloaded at the clinical research unit during scheduled site visits, as indicated in the Schedule of Assessments.
- h. Subjects will be given insulin usage diaries during the Lead-in Period and at the beginning of Weeks 1 through 4, 8, 12, 16, and 20. For one week of the Lead-in Period and Weeks 1 through 4, daily insulin use (short-acting, long-acting, and infusional as applicable) will be collected over seven days. For Weeks 8, 12, 16, and 20, daily insulin will be collected over a period of 3 consecutive days within that respective week.
- i. The *WHO-5 Well-Being Index & T1-DDS QOL* Questionnaires will be completed by the subjects at the Baseline, Day 84, and Day 161.
- j. Both the Liver MRI and FibroScan Baseline Assessments may be performed up to 7 days before the Day 1 Visit, after all other inclusion and exclusion criteria have been met.

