- g. FSH required at screening for post-menopausal women.
- h. Unblinded CGM will be performed for two weeks during the Lead-in Period (completed prior to the OBV), and throughout the study Dosing and Follow-up Periods from Dose 1 through the End of Study Visit. For on-going or newly enrolled subjects in Part A at the time of Protocol Amendment #2, CGM data will be collected throughout the study from Dose 1 through the Day 85/Week 13 Visit, and CGM devices will be “unblinded”. CGM data will be downloaded at the clinical research unit during scheduled site visits, as indicated in the Schedule of Assessments.
- i. Subjects will be given insulin usage diaries during the Lead-in Period and at the beginning of Weeks 1 through 4, 8, 12, 16, and 20. For both weeks of the Lead-in Period and Weeks 1 through 4, daily insulin use (short-acting, long-acting, and infusional as applicable) will be collected over seven days. For Weeks 8, 12, 16, and 20, daily insulin will be collected over a period of 3 consecutive days within that respective week.
- j. Blood ketones will be measured in the morning (prior to the subject's morning meal) 3 days a week – on an alternate day basis (e.g. Week 1: Study days 1, 3, and 5 or on Mondays, Wednesday, and Fridays) during the 12-Week Dosing Period (starting on Day 1 and continuing through the completion of Week 12), and once weekly throughout the Follow-up Period & EOS (Day 85 through Day 162) via finger-stick (strips for finger-stick measurement will be provided to the subjects). Subjects will be instructed to contact the investigator if they have positive ketones.
- k. The *WHO-5 Well-Being Index & T1-DDS QOL* Questionnaires will be completed by the subjects at the OBV, Day 84, and Day 161.
- l. No longer applicable for ongoing or newly enrolled subjects at time of the Protocol Amendment #1.
- m. **For ongoing or newly enrolled subjects at time of the Protocol Amendment #1:** overnight admission to the CRU at Week 13 & Week 24 will not occur.

For these visits, Week 13 procedures will be performed on Day 85, and Week 24 procedures will be performed on Day 162.

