5.2 Secondary Objectives

- To compare the effects of multiple doses of REMD-477 versus placebo on measures of glycemic control including change from baseline at Week 13 in fasting glucose and glucose area under the curve (AUC) after mixed meal tolerance test (MMTT) – Part A only.
- To compare the effects of multiple doses of REMD-477 versus placebo on change from baseline at Week 12 in average daily 24-h blood glucose concentration and time within target range as assessed by continuous glucose monitoring (CGM) and seven-point glucose profile.

- To compare the effects of multiple doses of REMD-477 versus placebo on the product of the ratio of average glucose (Week 12/Baseline) and ratio of average insulin use (Week 12/Baseline).
- To evaluate the safety and tolerability of multiple doses of REMD-477 versus placebo.
- To compare the incidence of hypoglycemic episodes after multiple doses of REMD-477 versus placebo.
- To compare the effects of multiple doses of REMD-477 versus placebo on change from baseline at Week 13 in hemoglobin A1c (HbA1c).
- To compare the proportion of subjects who achieve HbA1c reduction of $\geq 0.4\%$ after multiple doses of REMD-477 versus placebo at Week 13.
- To compare the effects of multiple doses of REMD-477 versus placebo on pancreatic beta cell function as measured by change from baseline at Week 13 in C-peptide AUC after a MMTT and arginine challenge test (for a subset of subjects who were enrolled prior to Protocol Amendment #1) – Part A only.
- To compare the effects of multiple doses of REMD-477 versus placebo on pancreatic alpha cell function as measured by change from baseline at Week 13 in peripheral levels of fasting glucagon, active and total glucagon-like peptide 1 (GLP-1), and glucagon and GLP-1 (active and total) AUC after MMTT – Part A only.
- To determine REMD-477 plasma concentrations and formation of anti-REMD-477 antibodies after multiple dosing.

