10.3.4.4 Continuous Glucose Monitoring and Seven-point Glucose Profile

The following mean and changes from baseline in parameters from the CGM and seven-point glucose profile assessment will be summarized separately for Parts A and B by treatment. For the Average Daily 24-h Glucose Concentration, the percentage changes from baseline will also be summarized separately for Parts A and B by treatment.

- Average Daily 24-h Glucose Concentration
 - Derived as the average 24-h glucose concentration, over the course of 7 days or 3 days, for CGM and seven-point glucose respectively.
- Time within Target Range (70-180 mg/dL), Time lower than Target Range (<70 mg/dL) and Time higher than Target Range (> 180 mg/dL)
 - Derived as the percentage of time for which the glucose concentration falls into these corresponding ranges, over the course of 7 days for CGM
 - Derived as the summation of time intervals where the glucose concentration falls into these corresponding ranges, divided by the total assessed time, and expressed as a percentage, for the seven-point glucose assessment.

The changes from baseline values will be statistically analyzed by part. For the Average Daily 24-h Glucose Concentration, the percentage changes from baseline will also be statistically analyzed by part. The baseline for CGM parameters is defined as the average value obtained from the Lead-In (Part A – 14 to 28 days; Part B – 7 to 14 days) period. The baseline for seven-point glucose is defined as the average obtained from the three consecutive days during the Lead-In (2 to 4 weeks) period.

A repeated measures ANCOVA will be used to compare the change from baseline values for the above parameters between treatment groups for each timepoint for Parts A and B separately. Dependent variables will be treatment, day, and the treatment by day interaction. The baseline variable will be used as a covariate. Covariates may be added to the above model depending on the results from the comparison of baseline characteristics as detailed in section [10.3.4.1](#).

Subject will be used as a random effect. The LS mean for each treatment will be presented for each timepoint. Also, the difference from placebo, the 95% CI of the difference from placebo, and p-value associated with the null-hypothesis of no difference will be reported for each timepoint.

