10.4.5 Incidence of Hypoglycemic Events

CGM will be conducted throughout the study from Dose 1 through EOS visit for safety monitoring and insulin use adjustments. The CGM data collected during this period will be analyzed separately for Parts A and B for the incidence of hypoglycemic events.

A hypoglycemic event is defined as an incident where the glucose value obtained from the CGM in a previous timepoint is higher than 70 mg/dL, but drops to 70 mg/dL or less in the subsequent timepoint with the low CGM glucose reading lasting at least 10 minutes. Each event will be counted even when multiple events occur on the same day, however if consecutive readings of GCM are deemed low then only a single event will be counted. The frequency of hypoglycemic events will be summarized by treatment group and timepoint (week). The categories for this frequency summary are as follows:

- Subjects with no hypoglycemic events
- Subjects with 1 to 5 hypoglycemic events
- Subjects with 6 to 10 hypoglycemic events
- Subjects with 11 to 15 hypoglycemic events
- Subjects with 16 or more hypoglycemic events

The same summary will be repeated for the second hypoglycemic threshold, where a hypoglycemic event is defined as an incident where the glucose value obtained from the CGM in

a previous timepoint is 54 mg/dL or higher, but drops below 54 mg/dL in the subsequent timepoint.

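### SAP 10.4.5 counts CGM hypoglycemic events only from Dose 1 and leaves the lead-in event rate unused, so with 25 per arm a chance baseline difference is neither shown in that table nor adjusted for

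*Protocol*

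**What the plan says.** Lead-in CGM is part of the design for every subject. For Part A, Protocol Appendix A (footnote h) states: "Unblinded CGM will be performed for two weeks during the Lead-in Period (completed prior to the OBV". For Part B, footnote g states: "Blinded CGM will be performed for one week during the Lead-in Period (completed prior to the Baseline Visit". On treatment, Part A wears CGM continuously, and Part B wears it "for one week after Doses 1, 4, 8 and 12". Within each Part the study device has the same setting before and after dosing: unblinded in A, blinded in B.

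SAP 5.2 lists as a secondary objective: "To compare the incidence of hypoglycemic episodes after multiple doses of REMD-477 versus placebo". SAP 10.4.5 sets the period for this endpoint: "CGM will be conducted throughout the study from Dose 1 through EOS visit for safety monitoring and insulin use adjustments". It continues: "The CGM data collected during this period will be analyzed separately for Parts A and B for the incidence of hypoglycemic events". The output is described as: "The frequency of hypoglycemic events will be summarized by treatment group and timepoint (week"), with subjects classed by event count (0, 1–5, 6–10, 11–15, 16 or more), and the table is repeated for the 54 mg/dL threshold. The section mentions no lead-in count, covariate, model, test or confidence interval.

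SAP 10.3.4.4 does use the lead-in for other CGM measures: "The baseline for CGM parameters is defined as the average value obtained from the Lead-In" period. Average glucose and percent time in, below and above 70–180 mg/dL are analyzed as change from that baseline, with baseline as a covariate.

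**The concern.** The drug is meant to lower insulin needs, and hypoglycemia is the event that readers will look for in each arm. If people differ in how often they go low, and some of that difference persists from lead-in to treatment, three arms of 25 can start with different event rates by chance. A table that begins at Dose 1 cannot separate that starting difference from a difference caused by treatment. The data that would separate them are already collected.

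At stake are the precision of a secondary comparison and the reader's ability to recognize an unlucky allocation. The two Parts are reported separately (SAP 10.1), so pooling does not help, and the protocol's Randomization section names no stratification factor.

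**Working it through.** **The plan's own figure.** No sample size or precision is stated for hypoglycemia. The 25 per arm comes from the primary endpoint (SAP 8: CV 36%, difference 30%, power 0.80, alpha 0.05). Two-sided normal formula: n = 2 × [0.36 × (1.960 + 0.842) / 0.30]² = 22.6, against the stated 22 or more; power at 22 is 0.789. That figure reproduces to within rounding, but says nothing about event counts.

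**Assumptions for event counts.** The documents give no CGM event rate or variance. The only average event rate is two symptomatic episodes per week (Protocol section 2), so take m = 2 per week. Assume subject rates are gamma with between-subject CV 0.5 to 1.0, a period-to-period multiplier with CV 0.3, and Poisson counts. Lead-in L and on-treatment T are 2 and 12 weeks in Part A, and 1 and 4 weeks in Part B.

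**Chance imbalance with no drug effect** (40,000 simulated trials per setting, 25 versus 25):
- The 95% range of the lead-in rate ratio between two arms runs from 0.65–1.56 (Part A, CV 0.5) to 0.48–2.09 (Part B, CV 1.0).
- The on-treatment rate ratio runs from 0.70–1.43 to 0.53–1.90. It is at least 1.25 or at most 0.80 in 22–50% of null trials.
- If an unadjusted t-test were applied, it would reject in 4.7–4.9% of all null trials. Among trials whose lead-in rates differ with |t| > 1.5, it would reject in 9.6–22%. With the lead-in rate as covariate, that conditional figure is 3.8–4.6%.

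**Gain from the covariate.** Let v = (m × CV)². The variance of a subject's observed weekly rate over w weeks is V(w) = 1.09v + 0.09m² + m/w = 1.09v + 0.36 + 2/w. The covariance of lead-in and on-treatment rates is v. So ρ = v / √[V(L) × V(T)], and the SE ratio (adjusted to unadjusted) is about √(1 − ρ²).

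| Part | CV | v | V(L) | V(T) | ρ | SE ratio, formula | SE ratio, simulated |
|---|---|---|---|---|---|---|---|
| A | 0.5 | 1 | 2.45 | 1.62 | 0.50 | 0.86 | 0.87 |
| A | 1.0 | 4 | 5.72 | 4.89 | 0.76 | 0.65 | 0.64 |
| B | 0.5 | 1 | 3.45 | 1.95 | 0.39 | 0.92 | 0.93 |
| B | 1.0 | 4 | 6.72 | 5.22 | 0.68 | 0.74 | 0.73 |

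These figures are for the whole on-treatment period. SAP 10.4.5 tabulates single weeks. With T = 1, V(1) is 3.45 (CV 0.5) or 6.72 (CV 1.0), and the gain is smaller:
- Part A: √[1 − 1/(2.45 × 3.45)] = 0.94 to √[1 − 16/(5.72 × 6.72)] = 0.76.
- Part B: √[1 − 1/3.45²] = 0.96 to √[1 − 16/6.72²] = 0.80.

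**Why not a change score.** For equal windows, Var(change) = 2V − 2 × covariance, which exceeds V whenever the correlation is below 0.5. In Part B at CV 0.5, one week against one week: 2(3.45) − 2(1) = 4.90, against 3.45 for the raw count. Under a different assumption set (3 events per week, CV 0.6, true-rate correlation 0.7): V = 1.8² + 3 = 6.24, and the change has variance 2(6.24) − 2(0.7 × 3.24) = 7.94, about 27% larger.

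**The case against.** The strongest case on the other side has five parts.

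- **The table is descriptive.** SAP 10.4.5 plans no test or interval, and randomization keeps the arms comparable on average. A reader might infer that the plan will read chance imbalance as a drug effect, or that it inflates the false-positive rate. The documents do not support that: no error rate attaches to this output, and even a hypothetical unadjusted test holds its level over all allocations. This stands. What remains is imprecision, and a poor guide to the truth in the allocations that happen to be unbalanced.
- **Baseline hypoglycemia is not ignored.** Percent time below 70 mg/dL, from the same device, gets a lead-in-adjusted comparison with a 95% CI (SAP 10.3.4.4). It is therefore too strong to say that no output could reveal an imbalance, and the TFL shells are not among the documents. This also stands, within limits. That measure is duration rather than number of events, has no 54 mg/dL version, and is analyzed only after Doses 4, 8 and 12 and at Weeks 16 and 20, whereas the event table starts in Week 1. The baseline check in SAP 10.3.4.1 covers only insulin use and HbA1c.
- **Event counts are not the sole exception.** A reader might infer that every other CGM measure carries its baseline as a covariate. It does not: the glucose-by-insulin ratio product in SAP 10.3.4.4 is analyzed by ANOVA on treatment, with covariates added only if the baseline check calls for them.
- **The inputs are assumed.** Persistence of individual rates may be weaker than modeled, because from Day 1 subjects titrate toward 80–120 mg/dL, and some in Part A may reduce insulin at randomization. Lower persistence means less gain from the covariate.
- **A one-week lead-in is noisy.** This is true for Part B. It argues against change scores, but the covariate remains usable.

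**Conclusion.** The point holds as a recommended improvement to SAP 10.4.5; it does not threaten the validity of the trial. Lead-in CGM exists for all subjects by design, the event endpoint does not use it, and a secondary objective calls for a comparison with placebo. With 25 per arm in each separately reported Part, a chance difference in starting event rates could be mistaken for a drug effect or could mask one. The unadjusted comparison is unbiased on average.

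Under the stated assumptions (2 events per week, between-subject CV 0.5–1.0, period CV 0.3), adjustment for the lead-in rate brings the SE of the arm difference over the whole treatment period to 0.64–0.87 of unadjusted in Part A and 0.73–0.93 in Part B, and less far for single weeks. None of these rates or variances comes from the trial, so the direction of the gain is firmer than its size. The gap is confined to event counts at both thresholds; time below 70 mg/dL is already covered.

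**What to change.** Amend SAP 10.4.5 before database lock:

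1. Apply the same event rules (70 mg/dL or less, and below 54 mg/dL) to the lead-in CGM.
2. Show lead-in events per 7 days of CGM, by arm and Part, as a baseline row in each table.
3. Compare on-treatment event rates of each dose with placebo, with the subject's lead-in rate as a covariate. One suitable choice is a negative binomial model with log CGM wear time as offset, reporting the rate ratio and 95% CI.
4. State the period compared and how wear time is counted. SAP 10.4.5 describes CGM from Dose 1 through EOS for both Parts, but Part B has four one-week windows, and Part A subjects under Amendment #2 stop at Day 85.
5. Do not report counts as change from baseline.

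SAP section 12 records that the event definition was already revised after the first Part A interim, so date this change and record who had seen results by arm.

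The cost is SAP wording and modest programming on data already collected, with no added burden on subjects. The limitation is the noisy one-week baseline in Part B, which reduces the gain there.

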Appendix B. Pharmacy Guide

REMD-477

Packaging and Formulation

REMD-477 will be manufactured and packaged by a certified CMO and distributed using a GCP-compliant clinical study drug distribution procedures. REMD-477 is supplied as single-use glass vials formulated with 10mM sodium acetate, pH 5.2, 5% (w/v) sorbitol, 0.004% polysorbate 20 at a protein concentration of 70 mg/mL.

Placebo

Placebo will be presented in identical containers. The formulation of placebo is 10 mM sodium acetate, pH 5.2, 5% (w/v) sorbitol, 0.004% polysorbate 20

Labeling

Each single-use vial will list the study drug name, storage conditions, and the sponsor name. In compliance with regulations, it will also contain the statement, "New drug – Limited by Federal Law for Investigational Use."

Storage

The supplied REMD-477 must be stored at a temperature of –20°C or below and protected from light. Exposure of the material to temperatures outside these limits, except for warming prior to reconstitution and administration, may not occur and may result in the loss of activity. The clinical supplies must thaw overnight at 2 to 8°C in temperature-monitored refrigerators. Once thawed, vials should be transferred to room temperature and gently inverted to ensure mixing. Mixing may result in the formation of small bubbles, which is normal. Preparation of the clinical supplies should be performed using aseptic techniques and under sterile conditions.

All required drug preparation materials are listed at the end of this appendix with the catalog information.

Records of the actual storage conditions for REMD-477 during the period of the study must be maintained (e.g., records of the date and time and initials of person

checking, and the “working day” temperatures of the refrigerator used for storage of clinical study supplies, continuous temperature recordings, or regularly maintained temperature alarm systems used in conjunction with temperature recording).

REMD Biotherapeutics must be notified if any investigational product is exposed to excessive or uncontrolled temperatures, in which case possible replacement of the material will be considered. Each vial is designated for single use only, and is not to be used to treat more than 1 subject. Vigorous shaking of the vials may denature the protein in solution and should be avoided.

Preparation

The exact preparation of the study drug will be described in detail in a separate document provided to the site in the Pharmacy Binder.

Supply and Return of Drug

At study initiation and as needed thereafter, investigational product will be shipped to a responsible person (e.g., a pharmacist) at the Principal Investigator’s institution, who will check the amount and condition of the drug and enter these data into the Proof of Receipt Form and Investigational Product Accountability Record. The Proof of Receipt Form should then be faxed to REMD Biotherapeutics and the original retained at the site. At the end of the study, or as directed, all investigational product supplies will be returned to REMD Biotherapeutics.

Investigational Product Accountability

An Investigational Product Accountability Record for the investigational products mandated by the protocol must be kept current and should contain:

- the dates and quantities of investigational product received from REMD Biotherapeutics
- manufacturing lot number for investigational product received
- subject’s identification (subject number and initials)
- date and quantity of investigational product dispensed
- the initials of the dispenser
- dose preparation records

The Return of Investigational Product for Destruction Form must be completed and included in the shipment of used and unused investigational product to REMD Biotherapeutics. At the end of the study, the Final Investigational Product Reconciliation Statement must be completed and provided to REMD Biotherapeutics.

These inventories must be made available for inspection by an authorized REMD Biotherapeutics representative and regulatory agency inspectors. The Principal Investigator is responsible for the accountability of all used and unused clinical study supplies.

